9.7 End of Study

The end of study will be defined as the date of the last visit of the last subject. A summary of the End of Study report will be sent to Institutional Review Boards (IRBs), if required, within 12 months of the end of the study.

10 Randomization and Masking

10.1 Randomization

At Baseline (Day 1), eligible subjects will be randomized in a 1:1 ratio to 1 of 2 treatment arms:

- Emixustat, up to 40 mg (step-up titration)
- Placebo

Randomization will be stratified by DME status (DME vs. no DME) and will occur in a masked fashion according to a randomization scheme generated by an interactive web response system (IWRS). A randomization number will be assigned to each subject at this time. The screening number which was assigned when the subject enrolled will be the subject ID number for the remainder of the study

10.2 Masking

Study subjects, Investigators and their staff, and Sponsor personnel involved with the conduct and monitoring of the study will be masked to the identity of treatment until after the final database is locked. Emixustat and placebo will be identical appearing tablets, and each treatment will be packaged in identical, tamper-proof, blister packaging to maintain masking.

All subjects will receive masked replacement (resupply) kits provided through the IWRS. In order to maintain masking, subjects randomized to the placebo arm will be mock-titrated on the same schedule as those in the step-up titration arm.

Appropriate precautions must be taken to prevent unauthorized access to the randomization scheme. The decision to unmask a subject's treatment assignment is to be made by the Investigator only if the subject's safety requires it. The treatment assignment for an individual subject may be obtained through the IWRS only in the case of a medical emergency when identity of the treatment assignment is essential for the clinical management of the subject. The Investigator must make every effort to contact the Medical Monitor before unmasking the treatment assignment. If unmasking is required for emergency subject management, the Investigator must document the medical rationale for unmasking and forward the information to the Sponsor within 24 hours of unmasking without revealing to the Sponsor personnel the treatment assignment.

If a serious adverse event (SAE) is assessed as unexpected and related to study drug, and meets the requirement for expedited regulatory submission, the Sponsor's Drug Safety department will unmask the treatment assignment for the individual subject, if warranted. Expedited

reports will be submitted to regulatory authorities in accordance with applicable regulations. Expedited reports will also be distributed to Investigators without revealing the treatment assignment and will be submitted to IRB in accordance with institutional guidelines.

If emergency unmasking is required for any reason, the subject will be withdrawn from the study.

11 Study Treatments

11.1 Drug Dosage and Administration

11.1.1 Emixustat Hydrochloride

Study drug will be taken orally, QD, in the evening for 84 days. Subjects will receive 4 tablets per day as follows:

- Week 1 = 5 mg emixustat/day – two 2.5 mg tablets plus two placebo tablets
- Week 2 = 10 mg emixustat/day – two 5 mg tablets plus two placebo tablets
- Week 3 = 20 mg emixustat/day – two 10 mg tablets plus two placebo tablets
- Week 4 through Week 12 = 40 mg emixustat/day = four 10 mg tablets

11.1.2 Comparative Treatment (Placebo)

Subjects in the placebo group will undergo the same dosing regimen as the active treatment group with subjects taking 4 placebo tablets orally, QD, in the evening for 84 days. The placebo tablets will be identical in appearance to the emixustat tablets but with only inactive ingredients.

11.1.3 Dose Reduction

Subjects who do not tolerate dose escalations will be returned to and held stable at the last tolerated dose; after week 4, all subjects will be held at a stable dose for the remainder of the study. Dose reduction is available for subjects who do not tolerate dose escalations due to AEs that in the opinion of the investigator would otherwise lead to discontinuation of study drug. Dose reduction may be undertaken only once and is only available at Visit 4, Visit 5, or Visit 6.

11.1.4 Rescue Therapy

Rescue Treatment Criteria for PDR

All subjects will be eligible for PRP or anti-VEGF therapy for PDR in the study eye as of Day 29 (Visit 6) of the study if the following criterion is met:

- There is new NV or growth of NV of the retina, disc, angle, OR iris such that the NV is greater in extent than at Day 1 (Visit 2/Baseline).

Rescue Treatment Criteria for DME

All subjects will be eligible for therapy for DME in the study eye as of Day 29 (Visit 6) of the study if either of the following criteria are met:

- a. Development or worsening of DME as illustrated by an increase in central retinal thickness of ≥ 100 microns from any previous visit (as measured by the Investigator)
- b. A BCVA decrease of ≥ 10 letters from any previous visit that is deemed secondary to DME.

Subjects for whom it is determined that treatment with PRP, anti-VEGF therapy, or local corticosteroids in the study eye is necessary will discontinue study drug, be discontinued from the study, and undergo Early Termination assessments prior to any of these therapies.

PRP, anti-VEGF agent therapy, focal laser therapy, or local corticosteroid therapy in the non-study eye is allowed at any time, at the Investigator's discretion.

11.2 Supply, Packaging, Labeling, and Storage

Emixustat (2.5, 5, or 10 mg) tablets and placebo tablets will be packaged in identical, tamper-proof, blister packaging to maintain masking.

11.3 Measurement of Study Drug Adherence

Study drug will be taken orally, QD, in the evening, for 84 days. At each study visit, the subject will be queried regarding compliance with the treatment regimen.

11.4 Study Drug Accountability

The Investigator will maintain accurate records of inventory and dates of receipt of all study drug. In addition, accurate records will be kept regarding when and how much study drug is dispensed to each subject and how much is returned by each subject. Reasons for departure from the expected dispensing regimen must also be recorded.

For regulatory requirements regarding drug accountability, all unused study drug and opened, empty blister packaging from used study drug will be reconciled by the clinical research associate (CRA). Once reconciled, study drug can be returned to the Sponsor or designee according to applicable state and federal regulations.

If study drug is returned by the site, it must be accompanied by the appropriate documentation and be clearly identified by protocol number and study site on the outermost shipping container. Returned supplies should be in the original containers (eg, subject kits). The CRA

should facilitate the return of unused study drug and opened, empty blister packaging from used study drug.

If study drug is authorized by the Sponsor to be destroyed at the site, it is the Investigator's responsibility to ensure that arrangements have been made for the appropriate disposal. Written authorization should be issued by the Sponsor; procedures for proper disposal should be established according to applicable regulations, guidelines and procedures. Appropriate records of the disposal should be maintained.

11.5 Prior and Concomitant Therapy

In addition to the exclusion criteria, the following are excluded during the course of the study:

- Systemic use of a strong inducer of or a strong or moderate inhibitor of CYP2D6 (as listed in [Appendix B](#))
- Anti-coagulant therapy (eg, heparins, warfarin, other oral anti-coagulants). Anti-platelet therapy (eg, aspirin, clopidogrel) is allowed.
- Systemic anti-VEGF or pro-VEGF treatment

If elective, urgent, or emergency surgery is required at any time between randomization and Day 85, the investigator will confer with the Medical Monitor, who will determine if a temporary discontinuation of masked study drug is warranted before and/or after the surgery.

For subjects who undergo ocular treatments, procedures or surgeries (eg, retinal detachment surgery) with the potential to affect protocol assessments or disease outcomes, the Investigator should confer with the Medical Monitor to determine whether or not the subject should continue with study drug.

The Medical Monitor should be notified before prohibited medication or therapy (as listed in [Section 9.3](#) Exclusion Criteria and [Appendix B](#)) is administered unless the safety of the subject requires immediate action. The decision to administer a prohibited medication or therapy should be done with the safety of the subject as the primary consideration. The Medical Monitor will determine whether or not the subject may continue with study participation. The Investigator should contact the Medical Monitor if permissibility of a specific medication or therapy is in question to discuss whether or not the subject should continue with study participation.

12 Study Visits

The Schedule of Events is presented in [Appendix A](#). A detailed accounting of assessments performed at each study visit is presented below.

The scheduled visits include Screening (within 30 days prior to baseline), Baseline (Day 1), and days 8, 15, 22, and 29 (each ± 1 day) and days 57 and 85 (each ± 5 days). The Day 85 visit will be one day after the last drug/placebo treatment. The Study Exit visit will be performed 30 days (± 5 days) after the last dose of study drug.

12.1 Visit 1: Screening (≤ 30 days prior to Baseline [Day 1]):

The following procedures will be performed at Visit 1, Screening (≤ 30 days prior to Baseline [Day 1]):

- Explain the purpose and conduct of the study visits to the subjects, answer the subject's questions, and obtain written informed consent
- Review inclusion/exclusion criteria
- Obtain demographic data
- Obtain medical, surgical, and ocular history
- Review previous and concomitant medications
- Perform abbreviated physical exam including height and weight
- Obtain 12-lead ECG
- Obtain vital signs
- Blood sample for serum pregnancy test for women of childbearing potential
 - Blood samples for clinical chemistry, hematology (including glycosylated hemoglobin A1c [HbA1c]), and coagulation. (Note: Any laboratory screening test that meets the abnormality criteria stated in Exclusion Criterion No. 10 [Section 9.3, Exclusion Criteria] can be repeated once within the 30 day period from screening to baseline.)
- Urinalysis
- The following ophthalmic procedures will be performed:
 - NL-BCVA
 - Slit-lamp biomicroscopy

- IOP
- Gonioscopy
- Dilated ophthalmoscopy
- SD-OCT
- AEs
- Schedule subject to return for Baseline Visit (Day 1) within the specified window of time.

If the subject is not dosed by Day 30 of the 30-day screening period, the subject may be re-screened by repeating all of the screening procedures.

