	
µl sample of aqueous humor will be collected from the study eye by paracentesis and shipped the same day on dry ice.
 
A one week supply of study drug (5 mg emixustat or placebo) will be dispensed, and subjects will self-administer drug (4 tablets) orally, QD, in the evening for 7 (\pm 1) days. Adverse events (AEs) will be assessed.
 
At Visit 3 (Day 8 \pm 1), subjects return for study drug, review of concomitant medications, and assessment of AEs; each subject will receive a 1 week supply of double the dose received at Visit 2 (10 mg emixustat or placebo), to be dispensed for self-administration, orally, QD (4 tablets) in the evening for 7 days (\pm 1 day).
 
At Visit 4 (Day 15 \pm 1), subjects return for study drug, a review of concomitant medications, and assessment of AEs; each subject will receive a 1 week supply of double the dose received at Visit 3 (20 mg emixustat or placebo), to be dispensed for self-administration, orally, QD, in the evening, for 7 days (\pm 1 day).
 
At Visit 5 (Day 22 \pm 1), subjects return for study drug, a review of concomitant medications, and assessment of AEs; each subject will receive a 1 week supply of double the dose received at Visit 4 (40 mg emixustat or placebo), to be dispensed for self-administration, orally, QD (4 tablets) in the evening for 7 days (\pm 1 day).
 
Subjects who do not tolerate dose escalations due to AEs that, in the opinion of the investigator would otherwise lead to discontinuation of study drug will be returned to and held stable at the last tolerated dose (ie, dose reduction). Dose reduction may only be undertaken once and is only available at Visit 4 (Day 15), Visit 5 (Day 22), or Visit 6 (Day 29).
 
Masked, Fixed Dose Phase: At Visit 6 (Day 29 \pm 1), subjects return for study drug; a review of concomitant medications, urine pregnancy test (for women of childbearing potential), NL-BCVA, ophthalmic exams (slit lamp biomicroscopy, IOP, dilated ophthalmoscopy), SD-OCT, and retinal oximetry imaging (selected sites) will be performed. Each subject will receive a 4-week supply of study drug (40 mg emixustat or the last tolerated emixustat dose; or placebo), to be

--	---

dispensed for self-administration, orally, QD (4 tablets) in the evening for 28 days.

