At Visit 7 (Day 57 ± 5), subjects return for study drug; a review of concomitant medications, urine pregnancy test (for women of childbearing potential), NL-BCVA, ophthalmic exams (slit lamp biomicroscopy, IOP, dilated ophthalmoscopy), SD-OCT, and retinal oximetry imaging (selected sites) will be performed. Each subject will receive a 4-week supply of study drug (40 mg emixustat or the last tolerated emixustat dose; or placebo), to be dispensed for self-administration, orally, QD (4 tablets), in the evening for 28 days.

One day after the last dose of study drug, subjects return on Visit 8 (Day 85 ± 5 days) for a review of concomitant medications, and a urine pregnancy test (for women of childbearing potential) and vital signs recheck; samples for safety laboratory tests (including HbA1c) will be collected, and an abbreviated physical exam and 12-lead ECG will be performed; NL-BCVA and LL-BCVA will be measured, and ophthalmic examinations (slit lamp biomicroscopy, IOP, dilated ophthalmoscopy, gonioscopy), FA, color fundus photography, SD-OCT, and retinal oximetry imaging (selected sites) will be conducted. A 50 μ l sample of aqueous humor will be collected from the study eye by paracentesis and shipped the same day on dry ice.

Study Exit: A Study Exit visit will be performed 30 days (± 5 days) after the last dose of study drug. Concomitant medications will be reviewed and a urine pregnancy test (for women of childbearing potential), NL-BCVA, SD-OCT, and ophthalmic examinations (slit lamp biomicroscopy, IOP, dilated ophthalmoscopy) will be performed.

Rescue Treatment Criteria for PDR: All subjects will be eligible for PRP or anti-VEGF therapy for PDR in the study eye as of Day 29 (Visit 6) of the study if the following criterion is met:

- There is new NV or growth of NV of the retina, disc, angle, OR iris such that the NV is greater in extent than at Day 1 (Visit 2/Baseline).

Rescue Treatment Criteria for DME:

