12.2 Masked Dose Escalation Phase

12.2.1 Visit 2: Baseline (Day 1)

The following procedures will be performed at Visit 2, Baseline (Day 1):

- Review inclusion/exclusion criteria
- Review and update medical, surgical, and ocular history
- Review concomitant medications
- Randomization
- Obtain vital signs
- Urine pregnancy test (for women of childbearing potential)
- Blood sample for clinical chemistry, hematology, and coagulation. If screening laboratories were performed ≤ 14 days prior to Baseline (Day 1), these tests do not have to be repeated.
- Urinalysis. If screening laboratories were performed ≤ 14 days prior to Baseline (Day 1), this test does not have to be repeated.
- The following ophthalmic procedures will be performed:
 - NL-BCVA
 - LL-BCVA
 - Slit-lamp bio-microscopy

- IOP
- Gonioscopy
- Dilated ophthalmoscopy
- FA
- Color fundus photographs
- SD-OCT
- Retinal oximetry imaging (may be performed at selected sites)
- Aqueous humor collection (50 µl) from the study eye by paracentesis and shipped the same day on dry ice.
- AEs
- Dispense 1 week supply of masked study drug (5 mg emixustat or placebo) for subjects to self-administer 4 tablets (orally, QD, in the evening) for 7 days.
- Schedule subject to return for Visit 3 (Day 8 ± 1 day).

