12.3 Masked, Fixed Dose Phase

12.3.1 Visit 6 (Day 29 ± 1 day)

- Urine pregnancy test (for women of childbearing potential)
- Review concomitant medications
- The following ophthalmic procedures will be performed:
 - NL-BCVA
 - Slit-lamp biomicroscopy
 - IOP
 - Dilated ophthalmoscopy
 - SD-OCT
 - Retinal oximetry imaging (may be performed at selected sites)
- AEs
- Collect blister pack of study drug and review compliance

- Dispense a 4 week supply of drug (40 mg emixustat or the last tolerated emixustat dose; or placebo), to be dispensed by self-administration of 4 tablets (orally, QD, in the evening) for 28 days.

Note: Dose reduction is available for subjects who do not tolerate dose escalations due to AEs that in the opinion of the investigator would otherwise lead to discontinuation of study drug. The subject will be returned to and held stable at the last tolerated dose.

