12.3.2 Visit 7 (Day 57 ± 5 days)

- Urine pregnancy test (for women of childbearing potential)
- Review concomitant medications
- The following ophthalmic procedures will be performed:
 - NL-BCVA
 - Slit-lamp biomicroscopy
 - IOP
 - Dilated ophthalmoscopy
 - SD-OCT
 - Retinal oximetry imaging (may be performed at selected sites)
- AEs
- Collect blister packs of study drug and review compliance
- Dispense a 4 week supply of drug (40 mg emixustat or the last tolerated emixustat dose; or placebo), to be dispensed by self-administration of 4 tablets (orally, QD, in the evening) for 28 days.

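### Do the stated drug supplies run out before a late but in-window Visit 8?

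*Combined protocol and SAP*

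**What the plan says.** Section 12 (Study Visits) sets the late windows as "days 57 and 85 (each ± 5 days"), and then states: "The Day 85 visit will be one day after the last drug/placebo treatment". The Protocol Summary (Study Procedures) puts the two together: "One day after the last dose of study drug, subjects return on Visit 8 (Day 85 ± 5 days"). Appendix A repeats the rule under the Day 85 column.

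Section 11.3 fixes the course: "Study drug will be taken orally, QD, in the evening, for 84 days".

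Dispensing is described visit by visit:

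- Section 12.2.1 (Visit 2): "Dispense 1 week supply of masked study drug (5 mg emixustat or placebo) for subjects to self-administer 4 tablets". Sections 12.2.2 to 12.2.4 (Visits 3 to 5) each dispense one further week.
- Section 12.3.1 (Visit 6): "Dispense a 4 week supply of drug (40 mg emixustat or the last tolerated emixustat dose; or placebo"). Section 12.3.2 (Visit 7) dispenses the same amount, "to be dispensed by self-administration of 4 tablets (orally, QD, in the evening) for 28 days". Visit 7 is the last dispensing visit.

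Three other places bear on the point. Section 10.2 says all subjects get masked resupply kits through the IWRS, without a quantity. The Protocol Summary says "A one week supply of study drug (5 mg emixustat or placebo) will be dispensed", yet gives the dosing period on that pack as 7 days plus or minus 1. Section 11.4 requires records of what is dispensed and returned, and of reasons for any departure from the expected dispensing.

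**The concern.** Visit 8 supplies the only scheduled aqueous sample after baseline, and all eight primary biomarker changes depend on it. If a subject runs out of tablets and then attends late in the window, the sample is taken after several days off drug instead of one. Section 6.3 reports terminal half-lives of 4.6 to 7.9 hours in healthy subjects, so each extra day off drug spans 24/7.9 = 3.0 to 24/4.6 = 5.2 half-lives. With about 10 subjects per arm, uneven time off drug would be unwelcome noise. No passage tells a site what to do about dosing when an in-window visit falls after Day 85.

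**Working it through.** **Inputs.** Four 7-day supplies (Sections 12.2.1 to 12.2.4), two 28-day supplies (Sections 12.3.1 and 12.3.2), first dose on the evening of Day 1, Visit 7 on Days 52 to 62, Visit 8 on Days 80 to 90 (Section 12).

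**1. The plan's own figure.** 4 × 7 + 2 × 28 = 28 + 56 = 84 doses, covering Days 1 to 84. The next day is Day 85. The 84-day course, the supplies and the nominal visit date agree.

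**2. Other dates in the Visit 8 window.** Daily dosing to the evening before a visit on Day d needs d − 1 doses. The shortfall is max(0, d − 1 − 84).

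| Visit 8 day | Doses needed | Short by |
|---|---|---|
| 80–84 | 79–83 | 0 |
| 85 | 84 | 0 |
| 86 | 85 | 1 |
| 87 | 86 | 2 |
| 88 | 87 | 3 |
| 89 | 88 | 4 |
| 90 | 89 | 5 |

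With no spare doses, 5 of 11 dates are short, whether or not unused tablets are kept.

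**3. If packs hold spare doses (assumption; no count is given).**

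- One spare dose per weekly pack, as the Protocol Summary's 7 plus or minus 1 days might imply, with unused tablets not carried over: Visit 6 can be on Day 30 without a gap, so the latest Visit 8 with unbroken dosing is Day 30 + 28 + 28 = Day 86. Days 87 to 90 (4 of 11) stay short.
- The same spare with carry-over: 84 + 4 = 88 doses, enough for a visit on Day 89. Only Day 90 (1 of 11) stays short. Carry-over is the less natural reading, because packs are collected at each visit and the packs for Weeks 1 to 3 hold lower doses.
- s spare doses in each 28-day pack, Visit 6 on Day 29, no carry-over: the latest Visit 8 with unbroken dosing is Day 29 + 2 × (28 + s) = Day 85 + 2s, provided Visit 7 falls as late as its pack allows. For s = 0, 1, 2 and 3 this gives Days 85, 87, 89 and 90 (91, capped by the window).

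**4. Time off drug at the sample, no spare doses.** If dosing is unbroken to Day 84 and the visit is on Day 90, the gap is 90 − 84 = 6 days instead of 1. In the extreme case Visit 7 is on Day 52, leftovers are taken back, and the last dose is on Day 52 + 28 − 1 = Day 79. A visit on Day 90 is then 11 days later.

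**5. Can the one-day rule be met at all?** It needs Visit 8 − Visit 7 ≤ 28 + s. Of the 11 × 11 = 121 combinations of in-window dates, it fails in 10 + 9 + … + 1 = 55 for s = 0, in 5 + 4 + 3 + 2 + 1 = 15 for s = 5, and in none for s = 10. These are counts of date pairs, not probabilities. Every Visit 7 date leaves at least one in-window Visit 8 date that meets the rule (Day 80 after Day 52, any of Days 80 to 90 after Day 62).

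**The case for a change.** The case for acting is that the count is correct, that no passage states an overage, and that Section 10.2 gives no quantity for its resupply kits. A late visit is permitted, so a site could follow every instruction and still be unable to meet the one-day rule without undosed evenings earlier. A late Visit 7 does not cure this; it only moves the gap forward in time. A sentence or a cross-reference would close the point cheaply.

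The arithmetic stands, and so does the observation that the text is silent. What does not stand is the inference that the plan contradicts itself. The 84 doses are inferred from supply durations, so the shortfall depends on an assumption about packaging that the documents neither make nor exclude. The need for 85 to 89 doses also comes from reading the one-day rule as binding on every date in the window. Sections 11.3 and 15.1 describe an 84-day course, and nothing asks for dosing beyond it. A course a few days off nominal is what any visit window produces.

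The proposed gain is also thin. A listing of days from last dose to sample would describe time off drug without correcting for it. The protocol already needs the last-dose date to time the Study Exit visit, and Sections 11.3 and 11.4 already call for compliance queries, returned quantities and reasons for departures. An analyst who wants the interval can derive it.

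**Conclusion.** No change to the plan follows. If packs hold no spare doses, unbroken dosing is 1 to 5 doses short on 5 of 11 permitted Visit 8 dates. Under the two assumed readings with one spare dose per weekly pack, that falls to 4 dates without carry-over and 1 with it. The nominal schedule is internally consistent.

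No effect on the primary comparison is shown. Both arms follow the same masked visits and supplies, so a lapse in dosing has no evident route to a spurious difference. If a drug effect faded off treatment, a lapse would tend to shrink a true difference. How much cannot be said, because the documents give no time course for biomarker reversal.

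The conclusion rests on three points: actual pack and kit counts are not in these documents; the Study Manual and IWRS, where such detail would normally sit, are not available here; and visit timing is assumed to be similar in the two arms. If the kits turn out to hold no spare doses, the window, the supply and the one-day rule are for the sponsor to reconcile in its site instructions. No dosing or supply rule is suggested here.
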